12 MAY 2021

PROTOCOL NUMBER 2020089

PII

2020089

Table of Contents

1.	Title Page.....	1
2.	STUDY OBJECTIVE.....	3
3.	OVERALL STUDY DESIGN AND PLAN	3
4.	INCLUSION CRITERIA	5
5.	EXCLUSION CRITERIA.....	5
6.	CONTINUANCE CRITERIA	5
7.	IDENTITY OF INVESTIGATIONAL AND ACCLIMATION PRODUCT(S).....	5
8.	PRODUCT USAGE.....	5
9.	BLINDING, LABELING, AND SHIPPING PLAN	6
10.	METHOD OF ASSIGNING SUBJECTS TO TREATMENT GROUPS.....	6
11.	DETERMINATION OF SAMPLE SIZE	6
12.	SAFETY VARIABLES	6
13.	EFFICACY VARIABLE	7
14.	HYPOTHESES	8
	STATISTICAL AND ANALYTICAL PLANS	9
	APPENDIX.....	10

List of Abbreviations and Definition of Terms

Abbreviation	Definition
ADA	American Dental Association
AE	Adverse Event
CFR	Code of Federal Regulations
CRF(s)	Case Report Form(s)
FDA	Food and Drug Administration
GCP	Good Clinical Practices
IRB/IEC	Institutional Review Board/Independent Ethics Committee
OST	Oral Soft Tissue Exam
SOP	Standard Operating Procedure

2020089

1. Study Objective

The objective of this pilot study is to evaluate the effectiveness of denture gel at treating and preventing gum abrasions while eating peanuts.

2. Overall Study Design and Plan

This is a single center, two-treatment, parallel design study. Up to 40 subjects will be enrolled with a full mandibular and full maxillary denture with a history of food related abrasions.

At each visit, an Oral Soft Tissue exam, a Mucosa Condition Assessment and a Gum Abrasion Evaluation will be performed. At Baseline, the subjects will be randomized to a treatment group. At Baseline, Week 2, and Week 4 subjects will be asked to eat 20 grams of peanuts 4 times for a total consumption of 80 g of peanuts (subjects will be permitted to take breaks if needed and drink small sips of water). Following the peanut challenge, a licensed dental professional will re-evaluate the number and size of abrasions. Subjects will receive a consumer questionnaire to complete as well prior to the Baseline, Week 2, and Week 4 assessments.

Table 1. Study Schedule by Procedure Type and Visit

PROCEDURE	BASELINE	DAYS 3, 6	WEEK 2	WEEK 4
Informed Consent	X			
Medical History Review	X			
Demographics	X			
Inclusion/Exclusion Criteria	X			
Randomization	X			
Continuance Criteria		X	X	X
OST	X	X	X	X
Mucosa Condition Assessment	X	X	X	X
Pre-Peanut Gum Abrasion Evaluation	X	X	X	X
Product distribution/instruction	X			
Subject eats 80 g of peanuts (20g, 4 times)	X		X	X
Post-Peanut Gum Abrasion Evaluation	X		X	X
Questionnaire*			X	X
General Comments	X	X	X	X
AEs	X	X	X	X
Subject Accountability				X**

*This questionnaire will be analyzed outside of this protocol.

**Subject accountability will be completed after subjects complete the study at any time.

2020089

Prior to the Baseline, subjects will be asked to refrain from eating approximately 4 hours prior to their appointment. Previously screened subjects will review and sign an informed consent and receive a copy at the Baseline visit. The subjects' medical history will be collected or updated on site source documents. Demographic information and Inclusion/Exclusion Criteria will be obtained and documented on the appropriate case report form (CRF).

Subjects will be asked to remove their mandibular and maxillary full dentures and the dentures will be cleaned (if applicable) and examined by a dental professional. An OST will be performed followed by a Mucosa Condition Assessment, and a baseline pre-peanut challenge Gum Abrasion Evaluation.

Subjects will be asked to eat 20 grams of peanuts 4 times for a total consumption of 80 g of peanuts (subjects will be permitted to take breaks if needed and drink small sips of water). Additionally, subjects will be timed for each peanut challenge. If subjects are unable to finish the peanuts due to being too full or for any other reason, this will be noted in the eCRF General Comments. After completion of the peanut challenge, subjects will have a post-peanut challenge Gum Abrasion Evaluation.

Next subjects will be randomized to one of two treatments balanced on their baseline post-peanut challenge gum abrasion evaluations (area and number) mucosa condition, and age. The subjects will receive their products and site staff will review and provide written product use instructions.

Subjects will be reminded to refrain from eating approximately 4 hours prior to next visit.

Day 3, 6

Continuance criteria will be assessed. Subjects will be asked to remove their mandibular and maxillary full dentures and the dentures and subjects' mouths will be cleaned by a dental professional if applicable. An OST will be performed followed by a Mucosa Condition Assessment and then a Gum Abrasion Evaluation. Subjects will be reminded to refrain from eating approximately 4 hours prior to next visit.

Week 2

Continuance criteria will be assessed, and subjects will be asked to complete a questionnaire. Subjects will be asked to remove their mandibular and maxillary full dentures and the dentures and subjects' mouths will be cleaned by a dental professional if applicable. An OST will be performed followed by a Mucosa Condition Assessment and then a pre-peanut challenge Gum Abrasion Evaluation.

Subjects will then be asked to eat 20 grams of peanuts 4 times for a total consumption of 80 g of peanuts (subjects will be permitted to take breaks if needed and drink small sips of water). Additionally, subjects will be timed for each peanut challenge. If subjects are unable to finish the peanuts due to being too full or for any other reason, this will be noted in the eCRF General Comments. After completion of the peanut challenge, subjects will have a post-peanut challenge Gum Abrasion Evaluation. Subjects will be reminded to refrain from eating approximately 4 hours prior to next visit.

Week 4:

Continuance criteria will be assessed, and subjects will be asked to complete a questionnaire. Subjects will be asked to remove their mandibular and maxillary full dentures and the dentures and subjects' mouths will be cleaned by a dental professional if applicable. An OST will be performed followed by a Mucosa Condition Assessment and then a pre-peanut challenge Gum Abrasion Evaluation.

Subjects will then be asked to eat 20 grams of peanuts 4 times for a total consumption of 80 g of peanuts (subjects will be permitted to take breaks if needed and drink small sips of water). Additionally, subjects will be timed for each peanut challenge. If subjects are unable to finish the peanuts due to being too full or for any other reason, this will be noted in the eCRF General Comments. After completion of the peanut challenge, subjects will have a post-peanut challenge Gum Abrasion Evaluation. Subjects will return their kit boxes and will be dismissed from the study.

General Comments and Adverse Events, if applicable, will be recorded. Subject Accountability will be recorded as subjects are dismissed from the study at any point.

2020089

3. Inclusion Criteria

In order to be included in the study, each subject must:

1. Be 18 years of age;
2. Read, sign, and receive a copy of the Informed Consent prior to initiation of study procedures;
3. Have a full maxillary and mandibular denture and wear on a daily basis;
4. Have a history of food particles getting under their full denture and causing gum irritation;
5. Are willing to abstain from eating at least four hours prior to the visits;
6. Are willing to eat 4 X 20 grams of peanuts three times (Baseline, Week 2 and Week 4) without denture adhesive;
7. Clean their dentures on a daily basis;
8. Agree not to change their regular denture cleaning routine;
9. Agree to abstain from using denture adhesive during the study;
10. Agree to not participate in any other oral/dental product studies during the study.

4. Exclusion Criteria

Subjects are excluded from study participation if they:

1. Exhibit evidence of obvious oral pathology, as determined by the Study Dentist, as a result of a mandatory OST examination on the first day of the study;
2. Are allergic to any of the ingredients contained in the study product gel;
3. Are allergic to peanuts;
4. Wear dentures overnight;
5. Are insulin-dependent and/or have any health condition(s) which would prevent compliance with study procedures;
6. Are routinely using denture adhesive;
7. Present with any disease or conditions that could be expected to increase their susceptibility to gum abrasion (like diabetes or xerostomia); or
8. Present with any disease or conditions that could be expected to interfere with examination procedures or the subject's safe completion of the study.

5. Continuance Criteria

Subjects may be excluded from the study or the analysis if they:

1. Become intolerant to study procedures;
2. Develop insulin dependence and/or any health condition(s) which would prevent compliance with study procedures;
3. Did not abstain from eating at least four hours prior to the visits;
4. Have their denture altered during study;
5. Use denture adhesive;
6. Change their denture cleaning routine;
7. Wear their denture overnight;
8. Develop any disease or conditions that could be expected to increase their susceptibility to gum abrasion (like diabetes or xerostomia); or
9. Are non-compliant with the protocol.

6. Identity of Investigational Product(s)

- **Control:** Current Denture Care
- **Treatment:** Current Denture Care + Treatment Gel

7. Product Usage

Control Group:

Evening denture care:

2020089

In the evening subjects will perform their regular denture cleaning routine (if subjects brush their oral mucosa with brush, they will be allowed to continue doing so). They will be instructed to sleep without dentures.

Treatment Group:

Evening denture care:

In the evening subjects will perform their regular denture cleaning routine. They will be instructed to sleep without dentures.

Evening gel application:

Subjects will rinse out their mouth with water (if subjects brush their oral mucosa with brush, they will be allowed to continue doing so) and apply gel to their mucosa where they normally wear upper or lower denture.

Subjects will apply gel in the following order, reapplying gel onto the applicator each time:

- onto the mucosa (right half) under the upper denture
- onto the mucosa (left half) under the upper denture
- onto the mucosa (right half) under the lower denture
- onto the mucosa (left half) under the lower denture

Subjects will leave the gel overnight.

Subjects will not eat or drink anything in the evening after applying the gel.

8. Blinding, Labeling, and Shipping Plan

The take home kit boxes for the Control Group will contain a subject instruction sheet. The take home kit boxes for the Treatment Group will contain disguised and labeled gel, an applicator, and a subject instruction sheet. All instructions will be given (written and verbal). All labels will contain the study number, emergency phone number, distributor name/address, appropriate caution statements, and other information as required by internal regulations and clinical Standard Operating Procedures (SOPs). The shipping containers will be labeled with the "ship to" clinical site address and a "content statement" listing study number and number of kit boxes contained within. Supplemental product will be provided to the site.

9. Method of Assigning Subjects to Treatment Groups

Subjects who meet enrollment criteria will be stratified based on Baseline post-challenge number of lesions (< 1.6 vs. \geq 1.6), size of lesion (<16mm vs \geq 16mm), mucosa condition (\leq 1 vs. \geq 1), and age (\leq 64 vs. $>$ 64).

Subjects will then be randomized to one of the two (2) treatment groups using a balance and assignment procedure on site. This assignment process and the distribution of test products will be conducted in a protected area that will ensure blinding of the examiner to the identity of the test products. Product will be distributed according to a randomization schedule provided by the Sponsor. Product distribution and product return will be recorded on the Clinical Materials Inventory provided by the Sponsor. Subjects from the same household will be assigned to the same treatment group. The balance and assignment cut points may be adjusted during the study.

10. Determination of Sample Size

The sample size of 40 subjects was chosen for logistical reasons.

11. Safety Variables

Safety Observations and/or Measurements

Safety will be assessed by the absence of irreversible side effects.

Oral Examination

2020089

Assessment of the oral soft tissue is conducted via a visual examination of the oral cavity and perioral area utilizing a standard dental light, dental mirror, and gauze. The structures examined include the ridge, hard and soft palate, oropharynx/uvula, buccal mucosa, tongue, floor of the mouth, labial mucosa, mucobuccal/mucolabial folds, lips, and perioral area. All abnormal findings will be recorded and categorized by their location. An AE will be recorded if a new abnormal finding is noted after product distribution or any previously noted abnormal finding increases in severity during the treatment period. Subjects who experience an AE may be examined by the Medical Monitor, if necessary.

12. Efficacy Variable

Gum Abrasion Evaluation:

A dental professional will assess the gingiva for any gum abrasions. A periodontal probe will be used to measure the size of any presenting abrasions and will be documented in the eCRF. The gum abrasion will continue to be measured throughout the duration of the study to track healing of the abrasion.

Staining Procedure

Staining solution: Mira-2-Ton (Mira-2-Ton® Hager & Werken GmbH & Co. KG. Duisburg, Germany) – same batch of stain solution will be used through the whole study.

[figure not shown]
Prior to the staining oral mucosa will be dried with the air blast. Subjects will swish 5 mL of Mira-2-Ton dye for 10 seconds followed by 5 mL of water for 10 seconds as well.

Abrasion assessment

Prior to the assessment, the mucosa under the denture will be dried with the air blast. During the measurement, the size of each lesion (colored dark blue) will be measured using periodontal probe (assessing the length and width of the lesion). The location of the lesion(s) will also be documented on the diagram below, including whether the lesion is on the ridge or the mucosa (Pre-challenge Abrasion Evaluation). The assessment notes on Figure 1 below will be summarized into ECRF. All abrasion assessments will be carried out in the same quadrant ordering. Loosely attached discolorations will be excluded from evaluation. If examiner has difficulty with assessment (plaque or abrasion), she/he will carefully try to remove the staining (non-removable stains will be assessed as abrasion). After the peanut eating exercise (no adhesive period), subjects will be instructed to rinse out their mouth till all of the particles are removed and the oral mucosa under the denture will be re-stained again prior to the 2nd assessment (Post-challenge Abrasion Evaluation).

Figure 1 _ The location (and shape) of each gingival abrasion would be drawn on a maxillary and mandibular denture ridge chart.

2020089

The exact dimension (as measured with the periodontal probe) of the abrasion will be recorded. For analysis purposes, abrasion might be divided into the following categories:

- small, if $\emptyset \leq 2.5$ mm,
- medium, if $\emptyset > 2.5$, but ≤ 5 mm,
- large, if $\emptyset > 5$ mm.

Images (traditional or 3D) of abrasions might be taken for documentation and exploratory purposes.

Mucosa Condition Assessment:

The entire mucosal region under the denture will be assessed with one score per arch.

0 = pink firm tissue absent of redness and inflammation; 1 = mild redness or inflammation – slight change in color and little change in texture; 2 = moderate redness and/or inflammation – moderate glazing, redness, edema and hypertrophy 3 = severe redness and/or inflammation – marked redness and hypertrophy

13. Hypotheses

Treatment

Null Hypothesis: There is no difference between treatment groups for the abrasion endpoints (number of abrasions and size of abrasions, and mucosa assessment) across first 7 days after adjusting for the respective Baseline visit post-challenge abrasion endpoint.

Alternative Hypothesis: There is a difference between treatment groups in abrasion endpoints (number of abrasions and size of abrasions, and mucosa assessment) across first 7 days after adjusting for the respective Baseline visit post-challenge abrasion endpoint.

Prevention

Null Hypothesis: There is no difference between treatment groups for the abrasion endpoints (number of abrasions and size of abrasions, and mucosa assessment) across weeks 2 and 4 after adjusting for the respective Baseline visit post-challenge abrasion endpoint.

2020089

Alternative Hypothesis: There is a difference between treatment groups in abrasion endpoints (number of abrasions and size of abrasions, and mucosa assessment) across weeks 2 and 4 after adjusting for the respective Baseline visit post-challenge abrasion endpoint.

14. Statistical and Analytical Plans

To assess the impact of the product on the treatment of lesions, the average size of the Pre-challenge Abrasions (in mm) and the average Number of Pre-challenge Abrasions, and Mucosa Assessment across days 3 and 6 will be analyzed using a repeated measures analysis of covariance with factors in the analysis for treatment, day and respective baseline post-challenge lesion variable as the covariate. The treatment by baseline lesion and treatment by day interactions will be assessed at the 10% level. Additionally, the by day responses will also be carried out separately from the repeated measures model,

To assess the impact of the product on the prevention of lesions, the average size of the Pre-challenge Abrasions (in mm), the average Number of Pre-challenge Abrasions, and Mucosa Assessment across weeks 2 and 4 will be analyzed using a repeated measures analysis of covariance with factors in the analysis for treatment, week and respective baseline post-challenge lesion variable as the covariate. The treatment by baseline lesion and treatment by week interactions will be assessed at the 10% level. Additionally, the by week responses will also be carried out separately from the repeated measures model,

The size of the Pre-challenge Abrasions might be collapsed into pre-defined categories.

Additional analysis of the data might be carried out for exploratory purposes. If the data does not satisfy the normality assumption, then a non-parametric analysis will be utilized. All statistical tests will be two-sided with 10% Type I error rate.

Demographic data will be summarized for all subjects randomized in the study.

2020089

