APPENDIX

Adverse Event Reporting

Abnormal findings which may qualify as AEs are those that: 1) were not present at Baseline and occurred after product usages of any duration, or, 2) were present at Baseline and worsened in severity after product usage of any duration. All AEs will be recorded on the CRF. If a question should arise about the causal relationship of an AE to product usage, the Medical Monitor will be contacted to make the determination of relatedness.

An **unexpected** event is defined as one that is not identified in nature, severity, or frequency in the current safety assessment. The events will be reported to the FDA as required, upon receipt of pertinent clinical data and completion of the required forms.

Any clinically significant abnormal laboratory finding, serious or unexpected AE, or medical event which results in the withdrawal of a subject from the study, must be followed to resolution with appropriate medical management, or as deemed necessary (with the Sponsor's agreement).

Advertising

Any advertisements used in recruitment of subjects must receive prior approval from P&G and the Investigator's IRB. A copy of the IRB-approved advertising and the documentation thereof must be provided to P&G.

Data Collection

The Investigator has the responsibility for ensuring that all source documents (i.e., study and/or medical records) and CRFs are completed and maintained according to the study protocol and are available at the site.

Any biological samples collected from subjects will be stored by the P&G lab. After a time period of two years from the last study visit, any remaining samples will be discarded. The P&G lab will provide a statement of proof to the sponsor's Clinical Trial Manager.

Case Report Forms

The Data Manager will supply the paper and/or electronic CRFs to be used in this study. It is the responsibility of the Investigator to maintain and submit accurate and timely CRFs to the Sponsor. All hard copy CRFs will be filled out legibly in ink.

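### Stopping the gel or the peanuts is not separated from leaving the study, so later examinations are not provided for, and gel-related exits can occur in one arm only

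*Combined protocol and SAP*

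**What the plan says.** Section 5 (Continuance Criteria) opens "Subjects may be excluded from the study or the analysis if they" and then lists nine grounds. Criterion 1 is "Become intolerant to study procedures"; criterion 9 is "Are non-compliant with the protocol". At Days 3 and 6 and Weeks 2 and 4, Section 2 lists the continuance check first, ahead of the soft tissue, mucosa and abrasion examinations.

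On what is recorded, Section 2 ends with two sentences: "General Comments and Adverse Events, if applicable, will be recorded", then "Subject Accountability will be recorded as subjects are dismissed from the study at any point". The Appendix (Adverse Event Reporting) adds that a "medical event which results in the withdrawal of a subject from the study, must be followed to resolution", and asks the investigator for a final report that covers early withdrawals. Table 1 has no early-termination visit.

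The prevention outcomes in Section 14 are "the average size of the Pre-challenge Abrasions (in mm), the average Number of Pre-challenge Abrasions, and Mucosa Assessment across weeks 2 and 4". The treatment outcomes are the same three measures at Days 3 and 6. Sections 6 and 8 give gel to the Treatment arm only; the control kit holds an instruction sheet.

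**The concern.** Stopping a study procedure and leaving the study are different events, and the plan has no text that distinguishes them. A subject who stops the gel after Day 3, or declines the Week 2 peanuts, can still be examined at every remaining visit. If that subject is instead excluded under Section 5, the later values do not exist, and no choice of analysis set or missing-data method can observe them afterwards.

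The hypotheses in Section 13 compare randomised groups. If the chance of leaving depends on the arm and on the state of the mucosa, the subjects who remain at Weeks 2 and 4 are a selected group, and selected differently in the two arms. In a study of up to 40, a few such exits could shift the comparison.

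**Working it through.** **Which outcomes need the gel or the peanuts?**

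- Abrasion number and size: Section 14 analyses the pre-challenge evaluation. At Weeks 2 and 4 it comes before that visit's peanuts; at Days 3 and 6 there is no challenge.
- Mucosa score: Section 2 places it before the pre-challenge abrasion evaluation.
- None of the three requires that gel was used. All remain measurable after the gel or the challenge has stopped.

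**Which routes out exist, and in which arm?**

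- Gel: intolerance of it (read under criterion 1), or not following its evening application or the ban on eating and drinking afterwards (criterion 9), can arise in the Treatment arm only.
- Peanuts: intolerance of the challenge (criterion 1) can arise in both arms. Section 2 says of unfinished peanuts only that they are noted in General Comments.

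**What is lost?** A subject excluded at Day 3 or 6 supplies no prevention value. If exclusion follows the continuance check directly, that visit's examination can be lost too. A subject lost after Week 2 has supplied everything except Week 4.

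**Scale of the bias.** Section 10 gives 40 subjects for logistical reasons, with no effect size, SD or dropout rate, so there is no figure to reproduce. The test level (two-sided 10%) is from Section 14. Assumed here: 20 per arm, no true effect, controls complete, and k of 20 gel subjects lost whose outcomes are d SD worse than those of gel completers.

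- Bias = (k/20) × d, in SD, favouring gel.
- SE = √(1/20 + 1/(20 − k)).
- Type I error = Φ(bias/SE − 1.645) + Φ(−bias/SE − 1.645).

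| k lost | d (SD) | Bias (SD) | SE | Bias/SE | Type I error |
|---|---|---|---|---|---|
| 2 | 0.5 | 0.05 | 0.325 | 0.154 | 10.4% |
| 2 | 1.0 | 0.10 | 0.325 | 0.308 | 11.6% |
| 4 | 0.5 | 0.10 | 0.335 | 0.298 | 11.5% |
| 4 | 1.0 | 0.20 | 0.335 | 0.596 | 16.0% |

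**Precision.** The difference detectable with 80% power is (1.645 + 0.842) × SE: 0.786 SD at 20 v 20, 0.808 at 20 v 18 and 0.834 at 20 v 16. Lost power is modest; the selection is the larger problem.

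**The case against.** The strongest reply is that the plan is silent rather than wrong. Exclusion is discretionary, it may be from the analysis alone, no text forbids later examinations, and Section 2 says that the three examinations are done at each visit. Gel intolerance is not named anywhere and has to be read into criteria 1 and 9. This is a four-week pilot, and the fields of the accountability form are not visible, so date and reason of exit may already be captured. All of this stands. It limits the point to what the plan fails to provide for. It does not remove it, because discretion without a rule lets similar subjects be kept or dismissed differently.

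Four stronger readings are tempting and are not supported.

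- That dismissal leaves nothing but an accountability form. Comments, adverse events, follow-up of withdrawal-causing medical events and the final report are also provided for. Moreover, Section 2 uses the word dismissed for ordinary completion too, so the sentence on accountability is not itself a withdrawal rule. None of these records is stated to include an abrasion or mucosa examination, so the efficacy gap remains.
- That later outcomes will never be collected. This goes beyond the text, which does not provide for them but does not exclude them.
- That failing to eat the peanuts removes the subjects with the sorest gums. The text only has it noted, fullness is the one reason it names, and the route is open to both arms.
- That the bias can be put in lesions by using 1.6 as the mean. In Section 9 that is a cut point for the Baseline post-challenge count, whereas the analysed outcome is pre-challenge.

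A repeated-measures model could also recover part of a missing Week 4 value from an observed Week 2 value if it were likelihood-based, which Section 14 does not state. It has no prevention-phase value to work from for a subject lost at Day 3 or 6.

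Finally, a Week 4 value without a Week 2 challenge may not measure quite the same thing. That is a real cost of the remedy.

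**Conclusion.** The point holds as a gap in data collection that should be closed. The plan permits removal from the study on grounds that can differ by arm, and does not provide for the examinations that would keep the randomised comparison intact.

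The actual bias is unknown. The tabulated range is an illustration: it rests on assumed losses in the gel arm only, on leavers doing worse than completers, and on an unadjusted normal-approximation comparison of means. With one subject lost, the same formula gives a type I error of only 10.1% to 10.4%. If leavers did better than completers, the bias would run against the gel.

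**What to change.** Add to Sections 2 and 5:

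- A subject who stops the gel or the peanut challenge, but has not withdrawn consent, stays for the remaining scheduled OST, Mucosa Condition Assessment and pre-challenge Gum Abrasion Evaluation.
- A subject who is leaving altogether has these three assessments at the dismissal visit, if willing.
- The date and reason for stopping gel, for stopping the challenge and for leaving the study are recorded separately, in both arms.

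Reconcile criterion 1 of Section 5 with the Section 2 text under which unfinished peanuts are only noted. None of this settles when the gel or the peanuts should stop; that stays a clinical matter.

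The cost is protocol and consent wording and a few eCRF fields. The remaining visits are already scheduled; only a dismissal outside a scheduled visit would need an extra examination. Flag Week 4 values from subjects without a Week 2 challenge and examine them in a sensitivity analysis.

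### Section 5 lets randomised subjects be dropped from the analysis at discretion after randomisation, and Section 14 names no efficacy analysis set

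*Combined protocol and SAP*

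**What the plan says.** Section 5 opens with "Subjects may be excluded from the study or the analysis if they". It lists nine grounds: intolerance of study procedures, health events, eating before a visit, denture alteration, adhesive use, a changed cleaning routine, overnight wear, new susceptibility to abrasion, and finally "Are non-compliant with the protocol".

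Randomisation takes place at Baseline (Section 2). Table 1 has no Baseline mark for the continuance criteria. The first check is in the Day 3, 6 visit text, "Continuance criteria will be assessed", and it is repeated at Weeks 2 and 4.

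On blinding, Section 9 says that assignment and distribution are "conducted in a protected area that will ensure blinding of the examiner to the identity of the test products". Section 8 describes the kits: "The take home kit boxes for the Control Group will contain a subject instruction sheet", whereas "The take home kit boxes for the Treatment Group will contain disguised and labeled gel, an applicator, and a subject instruction sheet". Section 7 gives the treatment group duties that the control group does not have, beginning "Subjects will apply gel in the following order, reapplying gel onto the applicator each time", then leaving the gel on overnight and not eating or drinking afterwards that evening.

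Section 14 specifies a "repeated measures analysis of covariance with factors in the analysis for treatment, day and respective baseline post-challenge lesion variable as the covariate" for the treatment hypothesis, and a parallel model for prevention. It attaches no analysis set to either. Its only population statement is that demographics cover everyone randomised.

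**The concern.** Section 5 names exclusion from the analysis separately from exclusion from the study. A subject can therefore complete the visits, have data recorded, and still be left out of the efficacy result. The wording is permissive, the ninth ground is open-ended, and every decision falls after randomisation.

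The arms are not symmetric. Without a placebo gel, subjects know their arm, and only gel subjects have gel-use duties to breach, so the ninth ground can reach more of them. Some grounds, such as intolerance, adhesive use or denture alteration, plausibly go with the state of the gums.

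If exclusions differ by arm and relate to outcome, the retained groups are no longer comparable. The estimated gel effect is then biased, and the two-sided 10% error rate stated in Section 14 no longer holds.

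**Working it through.** **Inputs from the plan.** 40 subjects (Section 10, chosen for logistical reasons), two arms, two-sided tests at 10%, and ANCOVA on the baseline lesion variable (Section 14). The plan gives no power, SD, effect size or exclusion rate, so it has no figure of its own to reproduce.

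**Assumptions.** 1:1 allocation (20 per arm); normal outcome with SD 1; no true effect; baseline-outcome correlation ρ = 0.5, varied from 0.3 to 0.7; k gel subjects excluded. Each subject has an exclusion score s = r·y + √(1 − r²)·e, where y is the outcome (higher is worse), e is independent noise and r is the strength of selection. The k gel subjects with the highest s are dropped, and a single-visit ANCOVA is run on the rest.

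**Bias by hand, k = 2.** The two largest of 20 standard normal values have expected values 1.867 and 1.408, which sum to 3.275. Removing them shifts the mean of the other 18 by 3.275/18 = 0.182 SD. ANCOVA removes the part that baseline explains, so approximately

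bias ≈ r × 0.182 × (1 − ρ²).

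- Perfect selection (r = 1): 0.182 × 0.75 = 0.137 SD.
- Moderate selection (r = 0.5): 0.5 × 0.182 × 0.75 = 0.068 SD.

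**Simulation** (at least 40,000 trials per scenario; bias is in favour of the gel):

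| Scenario (ρ = 0.5 unless stated) | Bias, SD | Type I error |
|---|---|---|
| No exclusions | 0.00 | 10% |
| 2 gel, unrelated to outcome | 0.00 | 10% |
| 2 gel, r = 0.5 | 0.07 | 11% |
| 2 gel, r = 1 (upper bound) | 0.14 | 15-16% |
| 3 gel, r = 0.5 | 0.10 | 12% |
| 3 gel, r = 1 | 0.20 | 20% |
| 2 in each arm, r = 0.5 | 0.00 | 10-11% |
| 2 in each arm, r = 1 | 0.00 | 13% |
| 2 gel and 1 control, r = 0.5 | 0.03 | 10-11% |
| 2 gel, r = 0.5, ρ = 0.3 / 0.7 | 0.08 / 0.05 | 11% / 11% |
| 2 gel, r = 1, ρ = 0.3 / 0.7 | 0.17 / 0.10 | 16-17% / 13-14% |

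The simulated bias agrees with the hand formula. A version closer to the repeated-measures model averages two visits, with an assumed between-visit correlation of 0.7. For two gel exclusions it gives 0.06 single-visit SD and 11.3% (r = 0.5), and 0.13 SD and 15.5% (r = 1).

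**Scale.** The difference detectable with 80% power, unadjusted, is (1.645 + 0.842) × √(2/20) = 0.79 SD. With ANCOVA at ρ = 0.5 it is 0.79 × √(1 − 0.25) = 0.68 SD. The moderate bias of 0.07 SD is about a tenth of that (0.07/0.68 = 0.10), and the upper bound about a fifth (0.14/0.68 = 0.21).

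**The case against.** The strongest reply is that the realistic effect is small. Moderate selection moves the error rate by about one percentage point, and even that needs every exclusion to fall in the gel arm. Most grounds bind both arms. Under the null, failing to apply the gel cannot itself worsen the gums, so a link with outcome needs a shared patient factor or deliberate selection. Table 1 schedules no gel adherence check, so gel breaches may rarely be recorded. The continuance check is listed before each visit's evaluations, and Section 9 blinds the examiner. Dismissals are recorded under Subject Accountability, and the investigator's final report covers deviations and early withdrawals. In a pilot sized for logistics, with three endpoints under two hypotheses each tested at 10%, other sources of error are larger.

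Most of this stands as a limit on size, and the perfect-selection figures should be read only as a bound. It does not close the gap. Checking the criteria before that visit's evaluation does not prevent a later decision to leave a subject out of the analysis, once outcomes are known. Examiner blinding protects measurement; the plan does not say that the examiner decides exclusions, and a blinded examiner still sees outcomes. The accountability records are not required by arm. The other sources of error would be added to, not replaced.

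Choosing all randomised subjects as the primary set is indeed a choice of what to estimate. It is the choice that preserves the randomised comparison, and the per-protocol result remains available.

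**Conclusion.** The concern holds. Section 5 permits discretionary exclusion from the analysis after randomisation, on nine grounds, with no arm-blind decision stated, and Section 14 leaves the efficacy set undefined. This is a stated rule that can bias the result, not merely a missing detail.

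The likely size is modest: 0.05 to 0.10 SD and a type I error of 11-12% for two or three gel exclusions under moderate selection. The upper bound is 0.20 SD and 20%, for three exclusions under perfect selection. There is no bias if exclusions act alike in both arms or are unrelated to outcome. The exclusion counts, correlations and 1:1 split are assumptions; the figures show what the rule allows and do not show that it will happen. With about 20 per arm it matters mainly for results near the significance threshold. It should be fixed, chiefly because the fix is cheap.

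**What to change.** 1. **Section 5:** delete the words that extend exclusion to the analysis. Clinical withdrawal decisions stay unchanged.
2. **Section 14:** state that the primary efficacy analyses include all randomised subjects in their assigned arm, using every observed evaluation in the planned repeated-measures models, whether or not a continuance criterion was breached.
3. **Follow-up:** where a subject breaches a criterion but can remain under observation, keep collecting the scheduled evaluations. This limits the missing data that withdrawal on the same nine grounds would otherwise cause.
4. **Reporting:** list exclusions and withdrawals by arm and reason, including subjects with no post-baseline evaluation.
5. **Per-protocol:** keep as a sensitivity analysis only, with each exclusion decided and documented blind to arm and outcome before database lock.

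The cost is wording in two sections and the remaining visits of the few subjects concerned. The downside is some dilution of the gel effect. As an illustration, if 2 of 20 gel subjects gained nothing, the average effect would be 18/20 = 90% of the full effect, so 0.68 SD would become 0.61 SD. The per-protocol analysis would still show the result without them.
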